Clinical Trial Protocol: THR-1442-C-458

Study Title: A Phase 1, Open-label, Randomized, Two-period, Two-treatment, Crossover Study to Evaluate the Effect of Exenatide on the Pharmacokinetics and Pharmacodynamics of Bexagliflozin in Healthy Subjects

Study Number: THR-1442-C-458

Study Phase: 1

Product Name: Bexagliflozin tablets

IND Number: 103822103822

Indication: Type 2 Diabetes Mellitus

Investigators: Single Center

Sponsor: Theracos Sub, LLC

Sponsor Contact: [name].
Theracos Sub, LLC.
[name]
[contact]

Sponsor's Protocol Representative: [name]
[name]
[contact] [contact]
Email: [contact]

Medical Monitor: [name].
Translational Medicine Group, MGH
[name]
[contact] [contact]
Email: [contact]

	Date
Protocol V1.0:	19 April 2017

Confidentiality Statement

The information in this document is confidential information of Theracos Sub, LLC ("Theracos") and must not be disclosed, used, or copied except with prior written approval from Theracos or to the extent required by applicable local, state or federal laws, rules and regulations.

SYNOPSIS

Sponsor: Theracos Sub, LLC

Name of Finished Product: Bexagliflozin tablets

Name of Active Ingredient: Bexagliflozin

Name of Inactive Ingredients: Polyethylene oxide, glyceryl behenate, lactose monohydrate, poloxamer, microcrystalline cellulose, colloidal silicon dioxide, and magnesium stearate.

Name of Reference Therapy: Byetta[®]

Name of Active Ingredient of Reference Therapy: Exenatide

Name of Inactive Ingredients: metacresol, mannitol, glacial acetic acid, and sodium acetate trihydrate in water for injection.

Study Title:

A Phase 1, Open-label, Randomized, Two-period, Two-treatment, Crossover Study to Evaluate the Effect of Exenatide on the Pharmacokinetics (PK) and Pharmacodynamics (PD) of Bexagliflozin in Healthy Subjects.

Study Number: THR-1442-C-458

Study Phase: 1

Primary Objective:

To evaluate the effect of exenatide injection on the PK and PD of bexagliflozin.

Secondary Objective:

To assess the safety and tolerability of bexagliflozin when it is used in combination with exenatide.

Study Design:

This is a phase 1, single center, open-label, 2 × 2 crossover study designed to assess the effects of exenatide injection on the PK and PD of orally administered bexagliflozin tablets. Approximately 20 eligible healthy subjects will be randomly assigned to one of the two groups (1 or 2) with up to 10 subjects per group. Each group will receive both the treatments alternately, in a crossover fashion (two-period, two-treatment crossover design), with the two treatment periods separated by a 7-day washout period. In Treatment Period 1, subjects in Group 1 will receive a single oral dose of bexagliflozin tablets, 20 mg, alone 30 min before breakfast, and subjects in Group 2 will receive subcutaneous injection dose of exenatide at 10 µg twice a day (bid) with initial dosing 30 min prior to a single oral dose of bexagliflozin tablets, 20 mg, and 1 h before breakfast and followed by the second dosing of exenatide alone 1 h prior to evening meals. In Treatment Period 2, subjects in Group 1 will receive subcutaneous injection dose of exenatide at 10 µg bid with initial dosing 30 min prior to a single oral dose of bexagliflozin tablets, 20 mg, and 1 h before breakfast and followed by the second dosing of exenatide alone 1 h prior to evening meals and subjects in Group 2 will receive a single oral dose of bexagliflozin tablets, 20 mg, alone 30 min before breakfast. Clinical laboratory tests and safety monitoring will be conducted during both treatment

periods.

In treatment period 1, subjects will be admitted to the clinic on day 0, the day before dosing, and will stay in the clinic until 48-h post-dose. In treatment period 2, subjects will be admitted to the clinic on day 7, the day before dosing, and will stay in the clinic until 48-h post-dose. Blood samples for bexagliflozin plasma concentrations will be collected at each period at pre-dose and at 0.5, 1, 2, 3, 4, 5, 6, 8, 10, 12, 16, 24, 36, and 48 h post-dose.

Urine samples for PD (urinary glucose excretion) analysis will be collected at each period in 12 h batches at pre-dose (h -12 to 0), and at post-dose at 0 to 12 h, 12 to 24 h, 24 to 36 h, and 36 to 48 h.

Study Population:

Approximately 20 healthy subjects are planned.

Diagnosis and Main Criteria for Inclusion:

1. Male and female subjects who are between the ages of 18 and 65 years, inclusive, in good health based on medical history, physical examination (PE), electrocardiogram (ECG) and routine laboratory tests.
2. Subjects with body-mass index (BMI) between 18.0 kg/m² and 32.0 kg/m², inclusive.
3. Subjects who are non-smokers for at least 3 months prior to screening.
4. Subjects with adequate venous access at multiple sites in both arms.
5. Subjects who are willing and able to be confined to the clinical research facility as required by the protocol.
6. Subjects who have the ability to comprehend and who are willing to provide written informed consent in accordance with institutional and regulatory guidelines.

Test Product; Dose; and Mode of Administration:

Bexagliflozin tablets, 20 mg, oral administration.

Reference Therapy; Dose; and Mode of Administration:

Byetta[®] (Exenatide), 10 µg, bid, subcutaneous injection.

Duration of Treatment:

This is a phase 1, two-period, two-treatment, crossover study. Subjects will be screened within 21 days of the initiation of study drug dosing. Eligible subjects who consent to the study will be randomly assigned to 1 of 2 groups, each group will receive both the treatments alternately, in a crossover fashion (two-period, two-treatment crossover design), with the two treatment periods separated by a 7-day washout period.

Pharmacokinetics Variables:

The following PK parameters of bexagliflozin will be determined after each subject is dosed with bexagliflozin alone or the combination of exenatide and bexagliflozin.

C _{max}	Maximum observed plasma concentration
t _{max}	Time of maximum observed plasma concentration
λ _z	Terminal phase rate constant
t _{1/2}	Apparent terminal half-life

CL/F Apparent oral clearance

V_z/F Apparent volume of distribution

AUC_{0-t} Area under the plasma concentration-time curve from Time 0 to Time t (time of last quantifiable plasma concentration)

$AUC_{0-\infty}$ Area under the plasma concentration-time curve from Time 0 to infinity

AUC_{0-extr} % of $AUC_{0-\infty}$ due to extrapolation from t_{last} to infinity

Pharmacodynamics Assessments:

PD parameters include:

- Urinary glucose excretion (UGE)

Safety Assessments:

- Physical examinations (PE)
- Vital signs
- 12-lead ECG
- Clinical laboratory tests including blood chemistry and hematology parameters
- Urinalysis
- Adverse events

Statistical Methods:

Statistical analysis will be performed using Statistical Analysis Software SAS (SAS Institute Inc., USA). PK parameters of bexagliflozin will be calculated using non-compartmental analyses (NCA) of plasma concentration-time data. To assess the effect of co-administration of exenatide on the PK of bexagliflozin, analyses of variance (ANOVA) using a linear mixed-effects model will be fitted to the natural logarithmic transformation of PK parameters of bexagliflozin (C_{max} , AUC_{0-t} and $AUC_{0-\infty}$). The linear mixed-effects model will include subject as a random effect, and treatment, period, and sequence as fixed effects. The 90% confidence intervals will be constructed for the ratio of geometric means of PK parameters (C_{max} , AUC_{0-t} and $AUC_{0-\infty}$) when bexagliflozin is dosed in combination with exenatide versus when dosed alone, with 80-125% defined as the lack of interaction boundaries.

Descriptive statistics for the PK parameters C_{max} , t_{max} , $AUC_{0-\infty}$, AUC_{0-t} , AUC_{0-extr} , CL/F, V_z/F , λ_z , and terminal elimination half-life ($t_{1/2}$) will be tabulated by treatment. Means, standard deviations, medians, ranges (min, max) and geometric means and coefficients of variation will be presented for all PK parameters with the exception of t_{max} . Medians and ranges will be presented for t_{max} .

Descriptive statistics on the PD parameters will also be performed. Descriptive statistics will be used to describe any differences in UGE values between treatment groups.

Date of Original Protocol: 19 April 2017

Prepared in: Microsoft Word 2010

TABLE OF CONTENTS

SYNOPSIS.....	2
LIST OF ABBREVIATIONS AND DEFINITIONS OF TERMS.....	9
1 INTRODUCTION	11
1.1 Bexagliflozin for the Treatment of Type 2 Diabetes Mellitus.....	12
1.1.1 Summary of Nonclinical Data with Bexagliflozin.....	12
1.1.2 Summary of Clinical Data with Bexagliflozin.....	12
1.2 Glucagon-like peptide 1 receptor agonists (GLP-1 RAs) and Exenatide	12
2 STUDY OBJECTIVES.....	14
2.1 Primary Objective	14
2.2 Secondary Objective	14
3 INVESTIGATIONAL PLAN.....	15
3.1 Overall Study Design and Plan.....	15
3.2 Rationale for Study Design and Control Group.....	15
3.3 Study Duration and Dates	16
4 STUDY POPULATION SELECTION	17
4.1 Study Population.....	17
4.2 Inclusion Criteria	17
4.3 Exclusion Criteria	17
5 STUDY TREATMENT(S).....	19
5.1 Description of Treatment(s).....	19
5.1.1 Study Drug.....	19
5.1.2 Exenatide.....	19
5.2 Treatment(s) Administered	19

MedDRA	Medical Dictionary for Regulatory Activities
NCA	non-compartmental analysis
OADs	oral antidiabetes drugs
Pgp	p-glycoprotein
PD	pharmacodynamics
PK	pharmacokinetics
PR	the period of time from the onset of the P wave to the beginning of the QRS complex
QRS	the QRS complex is a name for the combination of three of the graphical deflections seen on a typical electrocardiogram
QT	the QT interval is a measure of the time between the start of the Q wave and the end of the T wave in the heart's electrical cycle
QTc	the corrected QT interval is a measure of the time between the start of the Q wave and the end of the T wave in the heart's electrical cycle.
RR	respiratory rate
SAE	serious adverse event
SD	standard deviation
SC	subcutaneous
SGLT1	sodium glucose cotransporter 1
SGLT2	sodium glucose cotransporter 2
SOP	standard operating procedure
RBC	red blood cell (count)
T _½	apparent terminal half-life
TEAE	treatment emergent adverse event
T _{last}	time of last measurable concentration
T _{max}	time to maximum observed plasma concentration
T2DM	type 2 diabetes mellitus
TG	triglycerides
UTI	urinary tract infection
WOCBP	women of childbearing potential

1 INTRODUCTION

The renal Na⁺/glucose transport protein SGLT2 actively transports extracellular glucose into cells using the driving energy of the transmembrane electrochemical potential for sodium ions. Individuals with disruptions in SLC5A2, the gene encoding SGLT2, exhibit prominent glucosuria in the absence of significant co-morbidities (Santer, Kinner et al. 2003, Kothare, Seger et al. 2012); (van den Heuvel, Assink et al. 2002)). The excretion of glucose in the urine of diabetic subjects in amounts comparable or greater than that seen in individuals harboring loss of functions mutations in SGLT2 has the potential to improve both fasting and postprandial hyperglycemia without increasing insulin secretion, causing weight gain, or inducing hypoglycemia.

Bexagliflozin, a candidate oral antidiabetic agent, is a potent and highly specific inhibitor of the SGLT2. Bexagliflozin elicits a prominent and predictable glucosuria as demonstrated in laboratory animals and in humans. Type 2 diabetes mellitus (T2DM) is a chronic metabolic disease. Patients with T2DM often require multiple drug therapy to control the hyperglycemia and other comorbidities. Glucagon-like peptide 1 receptor agonists (GLP-1 RAs) offer important benefits as monotherapies or in combination with other oral antidiabetes drugs (OADs), with low risk for hypoglycemia and significant weight loss by enhancing glucose-dependent insulin secretion, suppressing postprandial glucagon release, signaling satiety, and slowing gastric emptying.

Clinical pharmacokinetic (PK) studies have shown that the peak plasma bexagliflozin concentrations occurred between 3 to 5 h and thereafter declined in a biphasic manner with mean elimination half-life values ranging from 7.80 to 9.71 h. Bexagliflozin is cleared predominantly by metabolism to an inactive metabolite, bexagliflozin 3-O-glucuronide by the uridine diphosphate glucuronosyltransferase isoform 1A9 (UGT1A9) pathway. Extended release bexagliflozin tablet formulations were developed to provide greater than 75% release in approximately 8 h *in vitro*.

Exenatide is one of most commonly prescribed GLP-1 RAs and is administered subcutaneously (SC) twice daily (bid) for its relatively short half-life of 2.4 h. Exenatide is primarily eliminated by glomerular filtration and subsequent proteolytic degradation, thus, interactions involving cytochrome P450 (CYP450) isoenzymes or enzymes responsible for phase II metabolism are not expected. As enzymes responsible for phase II metabolism are responsible for the elimination of bexagliflozin, drug-drug interaction between bexagliflozin and exenatide is not expected ((U.S. Department of Health and Human Services February, 2012). However, because exenatide slows gastric emptying, the rate of absorption for concurrent orally administered medications may be altered (Hurren and Pinelli 2012) (Kothare, Seger et al. 2012). The objective of this study is to evaluate the effects of coadministering exenatide on the pharmacokinetics (PK) and pharmacodynamics (PD) of bexagliflozin tablets.

1.1 Bexagliflozin for the Treatment of Type 2 Diabetes Mellitus

Bexagliflozin is a highly specific inhibitor of sodium glucose cotransporter 2 (SGLT2) with an *in vitro* IC₅₀ of 2 nM or 0.9 ng/mL and a 2435-fold selectivity for human SGLT2 compared with sodium glucose cotransporter 1 (SGLT1). Details of the nonclinical and clinical findings are described in the Investigator's Brochure.

1.1.1 Summary of Nonclinical Data with Bexagliflozin

Bexagliflozin exhibits high permeability and is a potential Pgp (p-glycoprotein) substrate and inhibitor. It is not a significant inducer or inhibitor of cytochrome P450 isozymes and other transporters relevant for drug-drug interactions.

1.1.2 Summary of Clinical Data with Bexagliflozin

Following administration of bexagliflozin tablets in extended release formulations, t_{max} was reached between 3 to 5 h. A 20 mg bexagliflozin tablet produced exposure with a C_{max} of 176 ng/mL or 134 ng/mL and an AUC₀₋₂₄ of 1199 ng·h/mL or 1087 ng·h/mL in healthy subjects when dosing was after or before a meal, respectively.

The principal metabolites in humans are similar to those found in monkeys and are dominated by glucuronides of the parent compound, for which the AUC is >30% relative to parent bexagliflozin. Modest accumulation consistent with an extended half-life has been seen following multiple daily dosing. Following oral administration of radiolabeled bexagliflozin, >90% of the ingested radioactivity was recovered, 51% as fecal excretion and 41% as urinary excretion. In urine, bexagliflozin accounts for 1.5% of the dose; most of the radioactivity is excreted as bexagliflozin 3'-O-glucuronide. The largest fraction of the radioactivity in feces is due to bexagliflozin, accounting for about 30% of the administered dose.

The safety and tolerability of bexagliflozin in healthy or diabetic subjects was initially evaluated in a single-dose study of up to 100 mg, followed by treatment study in which doses ranged from 5 mg/d to 50 mg/d and up to 96 weeks of treatment were evaluated. Detailed information of bexagliflozin clinical experience and potential risks for study subjects are provided in the Investigator's Brochure.

1.2 Glucagon-like peptide 1 receptor agonists (GLP-1 RAs) and Exenatide

GLP-1 RAs are recommended as an option in patients with T2DM, typically as a second-line agent, particularly when weight loss or avoidance of hypoglycemia is a primary consideration in the therapeutic strategy. GLP-1 RAs reduce hyperglycemia and promote weight loss by enhancing glucose-dependent insulin secretion, suppressing postprandial glucagon release, signaling satiety, and slowing gastric emptying. In terms of safety, the most common adverse events seen in clinical trials with GLP-1 RAs are of gastrointestinal character; mainly nausea, vomiting and diarrhea. However, the incidence diminishes over time. Other identified risks include pancreatitis, immunogenicity, acute renal failure and

rapid weight loss. Exenatide is one of most widely prescribed GLP-1 RAs. It was approved in 2005 and is administered subcutaneously bid at a maximum approved dose in the United States of 10 µg. It is recommended to be taken within 60 minutes of the morning meal and within 60 minutes of the evening meal (approximately 6 hours or more apart).

After subcutaneous administration, exenatide is rapidly absorbed, usually reaching peak concentrations 2 h post administration. Peak plasma concentrations of exenatide after a 10 µg dose reach approximately 200 pg/mL. Exenatide is primarily eliminated by glomerular filtration and subsequent proteolytic degradation. After a single subcutaneous dose, it exhibits a short half-life of approximately 2.4 h. PK/PD modeling and empirical assessments from early clinical studies supported a twice daily dosing regimen. Because of its relatively short half-life, significant systemic accumulation is not observed with repeated twice-daily dosing.

2 STUDY OBJECTIVES

2.1 Primary Objective

- To evaluate the effect of exenatide injection on the PK and PD of bexagliflozin tablets.

2.2 Secondary Objective

- To assess the safety and tolerability of bexagliflozin tablets when it is administered in combination with exenatide injection.

3 INVESTIGATIONAL PLAN

3.1 Overall Study Design and Plan

This single center, phase 1, open-label, 2×2 crossover study is designed to assess the effects of exenatide injection on the PK and PD of orally administered bexagliflozin tablets. Approximately 20 eligible healthy subjects will be randomly assigned to one of the two groups (1 or 2) with up to 10 subjects per group. Each group will receive both the treatments alternately, in a crossover fashion (two-period, two-treatment crossover design), with the two treatment periods separated by a 7-day washout period. In Treatment Period 1, subjects in Group 1 will receive a single oral dose of bexagliflozin tablets, 20 mg, alone 30 min before breakfast, and subjects in Group 2 will receive subcutaneous injection dose of exenatide at 10 μg bid with initial dosing 30 min prior to a single oral dose of bexagliflozin tablets, 20 mg, and 1 h before breakfast and followed by the second dosing of exenatide alone 1 h prior to evening meals. In Treatment Period 2, subjects in Group 1 will receive subcutaneous injection dose of exenatide at 10 μg bid with initial dosing 30 min prior to a single oral dose of bexagliflozin tablets, 20 mg, and 1 h before breakfast and followed by the second dosing of exenatide alone 1 h prior to evening meals and subjects in Group 2 will receive a single oral dose of bexagliflozin tablets, 20 mg, alone 30 min before breakfast.

Clinical laboratory tests and safety monitoring will be conducted during both treatment periods.

In treatment period 1, subjects will be admitted to the clinic on day 0, the day before dosing, and will stay in the clinic until 48 h post-dose. In treatment period 2, subjects will be admitted to the clinic on day 7, the day before dosing, and will stay in the clinic until 48 h post-dose. Blood samples for bexagliflozin plasma concentrations will be collected at each period at pre-dose and at 0.5, 1, 2, 3, 4, 5, 6, 8, 10, 12, 16, 24, 36, and 48 h post-dose of bexagliflozin.

Urine samples for PD analysis will be collected at each period in 12 h batch at pre-dose (h - 12 to 0), and at post-dose of bexagliflozin at 0 to 12 h, 12 to 24 h, 24 to 36 h, and 36 to 48 h.

Sampling time was determined based on previous pilot PK and PD studies.

For the schedule of study events table, see [Appendix 1](#). For overall dosing schedule, see [Table 1](#).

3.2 Rationale for Study Design and Control Group

The primary goal of the study is to assess the safety, tolerability, PK and PD of orally administered bexagliflozin tablets when it is concurrently administered with exenatide injection in healthy subjects.

This study is designed to be a two-period, two-treatment, crossover study with a 7-day washout period (>10 plasma apparent terminal elimination half-lives for both bexagliflozin and exenatide). The crossover study will allow direct comparison of two treatments in the

same subjects. Such an approach eliminates the influence of difference in subject characteristics seen in parallel group design. The primary route for excretion of exenatide is glomerular filtration and subsequent degradation of peptide bonds. Thus, drug interaction involving CYP450 and phase II enzymes are not expected between bexagliflozin and exenatide. However, because of slowing of gastric emptying, exenatide is expected to alter the absorption of orally administered concomitant medications especially when exenatide is administered prior to co-administered drug, typically resulting in a minor reduction of maximum plasma concentration (C_{max}) and a prolonged time of maximum concentration (t_{max}). Drug exposures are not expected to be significantly altered. In order to observe the maximal potential effect of exenatide on the absorption rate of bexagliflozin, bexagliflozin will be administered orally 30 min after subcutaneous exenatide injection, at 10 μ g bid (the highest dose approved for use in the United States), meanwhile, the highest dose used (10 μ g bid exenatide injection in the United States) or intended to be used (20 mg bexagliflozin tablets) clinically will be selected.

Previous studies showed that the PK parameters after multiple dosing were consistent with those after single doses for both bexagliflozin and exenatide. Thus a single oral dose of bexagliflozin tablets will be administered to healthy subjects in this study to evaluate the potential drug-drug interaction between bexagliflozin and exenatide. In this protocol, the effect of bexagliflozin on PK/PD of exenatide injection will not be measured since the PK of exenatide injection is unlikely to be affected by CYP450 and phase II enzymes involved pharmacokinetic interactions.

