9.5 Statistical Analysis of Pharmacokinetic Variables

To assess the effect of co-administration of exenatide on the PK of bexagliflozin, analyses of variance (ANOVA) using a linear mixed-effects model will be fitted to the natural logarithmic transformation of PK parameters of bexagliflozin (C_{max} , AUC_{0-t} and $AUC_{0-\infty}$). The linear mixed-effects model will include subject as a random effect, and treatment, period, and sequence as fixed effects. The 90% confidence intervals will be constructed for the ratio of the least squares (LS) geometric means of PK parameters (C_{max} , AUC_{0-t} and

AUC_{0-∞}) when bexagliflozin is dosed in combination with exenatide versus when dosed alone, with 80-125% defined as the lack of interaction boundaries.

Descriptive statistics for the PK parameters C_{max}, t_{max}, AUC_{0-∞}, AUC_{0-t}, AUC_{0-extr}, CL/F, Vz/F, λ_z, and terminal elimination half-life (t_{1/2}) will be tabulated by treatment. Means, standard deviations, medians, ranges (min, max) and geometric means and coefficients of variation will be presented for all PK parameters with the exception of t_{max}. Medians and ranges will be presented for t_{max}.

A listing of derived PK parameters of bexagliflozin by Subject and Treatment Period will be provided.

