The proportion of $AUC_{0-\infty}$ due to extrapolation (AUC_{extr}) will be calculated and expressed as a percentage. $AUC_{0-\infty}$ values will be considered unreliable estimates if the AUC_{extr} is greater than 20% and will be excluded from summary tables but will be listed.

CL/F will be calculated as $Dose/AUC_{0-\infty}$.

V_z/F will be calculated as $Dose/(\lambda_z \times AUC_{0-\infty})$.

$T_{1/2}$ will be calculated as $0.693/\lambda_z$.

Descriptive statistics for the plasma concentrations of bexagliflozin by Treatment and Timepoint will be provided. Listings of plasma concentrations by Subject Number, Treatment Sequence/Treatment, Period, and Timepoint will also be provided.

To assess the effect of co-administration of exenatide on the PK of bexagliflozin, an analyses of variance (ANOVA) using a linear mixed-effects model will be fitted to the natural logarithmic transformation of PK parameters of bexagliflozin (C_{max} , AUC_{0-t} and $AUC_{0-\infty}$). The linear mixed-effects model will include subject as a random effect, and treatment, period, and sequence as fixed effects. The 90% confidence intervals (CIs) will be constructed for the ratio of the least squares (LS) geometric means of PK parameters (C_{max} , AUC_{0-t} and $AUC_{0-\infty}$), when bexagliflozin is dosed in combination with exenatide versus when dosed alone, with 80-125% defined as the lack of interaction boundaries.

The ratios of geometric least squares means and corresponding 90% CI for the treatment comparison will be determined by exponentiating the mean differences between treatments on the logarithm scale. The intra-subject geometric CV%, $100\% * \sqrt{\exp(residual) - 1}$, where residual = the residual variance component and where exp is the natural exponential function, will be reported.

The appropriateness of the mixed model will be assessed through residual analyses. Any modifications required due to poor fit will be reported and executed.

Descriptive statistics for the PK parameters C_{max} , T_{max} , $AUC_{0-\infty}$, AUC_{0-t} , CL/F, V_z/F , λ_z , and $T_{1/2}$ will be tabulated by treatment. Means, standard deviations (SD), medians, ranges (minimum; maximum), and geometric means and coefficients of variation (CV) will be presented for all PK parameters with the exception of T_{max} . Medians and ranges will be presented for T_{max} .

A listing of derived PK parameters by Subject Number, Treatment Period, and Treatment will be provided.

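### The predicted delay in bexagliflozin t_max is summarised only by a median and range per treatment, so the crossover gives no within-subject estimate or precision for it

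*Protocol*

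**What the plan says.** Protocol 1 and 3.2 do not expect a metabolic interaction. The route they leave open is slower gastric emptying. For oral drugs given after exenatide, 3.2 describes this as "typically resulting in a minor reduction of maximum plasma concentration" "and a prolonged time of maximum concentration", and adds: "Drug exposures are not expected to be significantly altered". The tablet follows the injection by 30 min "In order to observe the maximal potential effect of exenatide on the absorption rate of bexagliflozin", a rationale that SAP 6.3.2 repeats. On the crossover, 3.2 says: "The crossover study will allow direct comparison of two treatments in the" same subjects.

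In the analysis (Protocol 9.5, SAP 7.2), a mixed model on the log scale gives 90% intervals for the ratios of C_max, AUC0-t and AUC0-inf "when bexagliflozin is dosed in combination with exenatide versus when dosed alone, with 80-125% defined as the lack of interaction boundaries". The code in SAP Appendix 2 names log AUC and log C_max as the responses. For t_max the SAP says: "Medians and ranges will be presented for" t_max. Derived parameters are also listed by subject, period and treatment. Neither document defines a within-subject t_max difference, an interval for one, or a size of delay that would matter.

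**The concern.** The rationale names an effect on absorption rate and times dosing to make it as large as possible. Of the measures reported, t_max shows timing most directly, and the protocol predicts that it will move. Each subject with two evaluable periods supplies a pair of t_max values, but the planned summary treats the two treatments as separate columns. A difference between two medians is not the median within-subject difference, has no interval, and ignores period.

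The stake is modest. If the delay is small, or is mainly a lag before absorption starts, C_max and AUC can sit inside the bounds. The report would then give the predicted effect no estimate and no statement of how well it was measured.

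**Working it through.** There is no planned figure to reproduce. Protocol 9.2 and SAP 3.5 say the sample size has no formal statistical basis, and no CV or t_max precision is stated.

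**Inputs from the documents.** Half-life 7.80 to 9.71 h and t_max 3 to 5 h (Protocol 1). Sampling at 0.5, 1, 2, 3, 4, 5, 6, 8, 10, 12, 16, 24, 36 and 48 h (Protocol 6.6.2.4). Twenty subjects, with replacement aimed at no fewer than 8 evaluable per group, so 16 in all (Protocol 5.4).

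**Assumed.** One-compartment kinetics and within-subject CV of 10-30%.

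**Step 1: slower first-order absorption.** In this model C_max is proportional to exp(-ke × t_max), with ke = ln 2 / half-life. A delay of d hours gives a C_max ratio of exp(-ke × d), whatever the starting t_max, and leaves AUC0-inf unchanged. Here ke = 0.693/7.80 = 0.0889 per h, or 0.693/9.71 = 0.0714 per h.

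| Delay | Ratio, half-life 7.80 h | Ratio, half-life 9.71 h |
|---|---|---|
| 1 h | 0.915 | 0.931 |
| 2 h | 0.837 | 0.867 |
| 3 h | 0.766 | 0.807 |

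**Step 2: lowest observed ratio that passes.** This is 0.80 × exp(t(0.95, n-2) × s_w × sqrt(2/n)), with s_w² = ln(1 + CV²). For n = 20 and CV 15%, s_w = 0.149 and t = 1.734, so the exponent is 1.734 × 0.149 × 0.316 = 0.082 and the limit is 0.80 × 1.085 = 0.868.

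| CV | n = 20 | n = 16 |
|---|---|---|
| 10% | 0.845 | 0.851 |
| 15% | 0.868 | 0.878 |
| 20% | 0.892 | 0.905 |
| 25% | 0.916 | 0.933 |
| 30% | 0.940 | 0.960 |

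At n = 20, the ratio for a 1 h delay clears the limit up to a CV of about 25% (at 25%, 0.931 passes and 0.915 just misses). The ratio for 2 h clears it only at 10% with the longer half-life. The ratio for 3 h never does. These limits apply to the observed ratio, so a true ratio close to the limit passes only about half the time.

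**Step 3: lag-type delay.** A pure lag leaves true C_max and AUC0-inf unchanged. Trials were simulated on the protocol's grid, 500 per scenario. Further assumptions were half-life 8.7 h, reference t_max 4 h, between-subject CVs of 20-30%, within-subject absorption-rate variation of 20% and assay noise of 10%. The bounds were applied to C_max and AUC0-t; AUC0-inf was not simulated. At n = 20 and CV 15%, the share meeting both bounds was:

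- no lag: 98.6%
- 1 h lag: 99.2%
- 2 h lag: 98.0%
- 3 h lag: 95.6%

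The criterion hardly responds to a lag. For a 2 h lag the share was 100% at CV 10%, 86% at 20% and 63% at 25%, and 92% at n = 16 with CV 15%. The fall at higher CV comes from imprecision. In the same simulation, slower absorption with a mean estimated t_max shift of about 0.7 h met the bounds in 90% of trials, and about 1.3 h in 51%.

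**Step 4: what the medians show.** A second simulation under similar assumptions (n = 20, 1000 trials) compared the two planned medians. With a 2 h lag they differed by at least 1 h in about 99% of trials (mean difference 1.8 h). With a 3 h lag they always did. With a 2 h delay from slower absorption they did in 91%.

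**Step 5: what a paired analysis adds.** For a 2 h lag, at n = 20 and CV 15%, the Hodges-Lehmann estimate averaged about 1.9 h with a mean 90% interval width of 1.5 h. The interval lay above zero in 98% of trials (94% at n = 16). For a 1 h lag it did so in 48% (42% at n = 16). This version used simple paired differences with no period effect simulated.

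**The case against.** The strongest reply is that t_max is already reported. A delay of 2-3 h would show in the medians (step 4), and the listing holds every paired value. Concentrations are also summarised by treatment and time point, which would display a delayed profile. C_max, which has the full interval treatment, is itself partly sensitive to absorption rate, and Protocol 3.2 predicts its fall in the same sentence as the longer t_max. Near 1 h, where the medians are weakest, the paired interval excludes zero in under half of simulated trials. All of this stands. It limits the point to a missing estimate and a missing measure of precision.

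A reader might go further and infer that the sponsor could declare no interaction at all despite an obvious delay. The documents do not support that. The clause "with 80-125% defined as the lack of interaction boundaries" is tied by name to C_max and the two AUCs, SAP 3.3 plans no formal hypothesis testing, and no rule turns the ratios into an overall declaration.

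A reader might also take t_max to be the variable the design was built around. The primary objective is PK and PD in general, and 3.2 justifies the crossover by the removal of between-subject differences.

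**Conclusion.** The point holds in limited form. The plan predicts a longer t_max and sets dosing to bring out an effect on absorption rate, but it gives no within-subject estimate or interval for the t_max shift. On the stated half-lives, a delay of about 1 h from slower absorption, or a lag of up to 3 h, can occur with C_max and AUC inside 80-125%. A delay of about 3 h from slower absorption would usually fail on C_max.

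These sizes rest on one-compartment kinetics and an assumed within-subject CV. At higher CV, fewer trials meet the bounds whether or not there is a delay. That t_max has only a descriptive summary rests on the text alone. The gap does not undermine the planned C_max and AUC comparisons; it leaves a predicted effect without an estimate that data already being collected could supply.

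**What to change.** Add to Protocol 9.5 and SAP 7.2:

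- The within-subject t_max difference, combination minus alone, from actual sampling times, for all subjects with both periods evaluable (20 planned, minimum 8 per group).
- A Hodges-Lehmann median shift with a 90% interval based on period differences by sequence. Take period 1 minus period 2 for each subject, estimate the shift of Group 2 relative to Group 1, and halve the estimate and its limits. Group 2 receives the combination first, so a positive value means a delay, and a common period effect cancels.
- A sentence saying that the 80-125% result covers C_max and AUC only, with the t_max shift reported beside it as the result on absorption timing.

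The cost is one SAP paragraph and one table line, with no new subjects or samples. The interval will be coarse, because sampling is hourly from 1 to 6 h and then every 2 to 4 h up to 16 h, and a shift of 1 h will often not be resolved. Reporting the interval makes that limit visible.
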